### 8.1.2 Form

Tretinoin Capsules are available as:

10 mg: Two-piece hard gelatin capsule with brown opaque cap and dark yellow opaque body, filled with yellow viscous oily suspension. Imprinted in black ink with stylized barr 808. Available in bottles of 100 capsules (NDC 0555-0808-02).

### 8.1.3 Storage and Stability

Store at 20° to 25°C (68° to 77°F) [See USP Controlled Room Temperature]. Dispense in a tight, light-resistant container as defined in the USP, with a child-resistant closure (as required). It is permissible for DF/HCC site to dispense ordered quantity of tretinoin in standard amber prescription bottle.

KEEP THIS AND ALL MEDICATIONS OUT OF THE REACH OF CHILDREN.  
PROTECT FROM LIGHT.

### 8.1.4 Availability

Tretinoin is commercially available.

### 8.1.5 Administration

Tretinoin will be administered by trained medical personnel at the investigational site. Treatment compliance will be monitored through documentation of study treatment administration in the subject's medical record.

Doses of tretinoin at initial and subsequent dosing should use actual (not ideal or adjusted) body weight for calculation of dose. The higher dose of an uneven dose will be the AM or morning dose.

Tretinoin will be administered orally as an outpatient in two divided daily doses (no in clinic dosing is required). The drug should be taken with food (ideally fat-containing to promote absorption). The dose each day of therapy should be given roughly 12 hours apart  $\pm$  30 minutes (suggested timing: 8:00 AM and then again at 8:00 PM daily). Participants should try to avoid shortened or prolonged dosing intervals when possible. If a dose of tretinoin is missed by  $\geq$  6 hours from the last oral dose,

then the next dose should be retimed for the morning of the following day. Any dose of tretinoin that was missed less than 6 hours from the last administration should be taken, and the following dose retimed for the morning of the following day. If tretinoin is not tolerated, or vomiting results in loss of the ingested dose, the dose should be skipped, and the next planned dose attempted when possible. The study drug may be crushed, chewed, or dissolved if necessary.

At each study or on-treatment visit (occurring every 28-days or every cycle), the dose of tretinoin should be recalculated again if there is > 5% change in body weight or body surface area (BSA) per institutional standard practice. Additional intravenous hydration is not required at study visits. An observation period is not required since dosing occurs outside the clinic setting.

#### 8.1.6 Ordering

Tretinoin, 10 mg capsules will be sourced locally by DF/HCC pharmacy site, and DF/HCC pharmacy site will be reimbursed via study fund.

#### 8.1.7 Accountability

The investigator, or a responsible party designated by the investigator, should maintain a careful record of the inventory and disposition of the tretinoin, using the NCI Drug Accountability Record Form (DARF) or another comparable drug accountability form (See the NCI Investigator's Handbook for Procedures for Drug Accountability and Storage).

#### 8.1.8 Destruction and Return

Unused and expired supplies of tretinoin will be destroyed on site per institutional SOP.

### 9. BIOMARKER, CORRELATIVE, AND SPECIAL STUDIES

Background information on the pre-clinical and clinical rationale for these investigations is discussed in *Section 2.0* above.

Research blood sample collections should occur at the following time points: (1) at baseline, within 14 days prior to Cycle 1 Day 1 of protocol therapy (ideally as close to administration of Cycle 1 Day 1 therapy as possible), (2) at the beginning of every new Cycle, following C1 (expected to occur every 28-days) for the first 12 cycles or 1 year on treatment.

If tumor is accessible by surgical or percutaneous approach, a tumor biopsy should be performed at the following time points: (1) at baseline, within 28 days of Cycle 1 Day 1 of protocol therapy (ideally as close to administration of Cycle 1 Day 1 therapy as possible) but *before* the administration of the first dose of study treatment. (2) After cycle 2 (8 weeks on treatment), within 14 days of the start of Cycle 3 Day 1 of protocol therapy – providing the procedure is considered safe, feasible, and accessible at the discretion of the treating investigator.

In all patients in whom a tumor deposit is safely accessible, a baseline tumor biopsy is required prior to the start of tretinoin treatment. In addition, an on-treatment biopsy will be required at after Cycle

2 (or 8 weeks into treatment), within 14 days of the start of Cycle 3 Day 1 of protocol therapy – providing the procedure is considered safe, feasible, and accessible at the discretion of the treating investigator. Patients may also be offered an end-of-treatment biopsy if the reason for discontinuation was progressive disease – again if safe and feasible.

### **9.1.2 Specimen Processing and Analysis**

Paired tumor biopsies of each participant will also be analyzed by ChIP- and ATAC-seq, to identify changes in *MYB* and *RAR $\alpha$*  binding to chromatin and evaluate chromatin accessibility at relevant regions; the goal is to study molecular changes that can be correlated with response to treatment. We have observed that *RAR $\alpha$*  protein levels are enhanced in the xenograft tumors that are treated with tretinoin for 28 days; as such, this enhancement would serve as an excellent marker of the action of the treatment on the tumor. Most patients in this study will also have had their tumor genomically characterized by a targeted next-generation sequencing platform (DFCI Oncopanel, formerly protocol#11-104, now #17-000) at the time of enrollment. Changes in *MYB* expression and *MYB* gene activation (translocation status) will be correlated with clinical response and patient outcomes. To identify mechanisms of resistance, we will use whole-exome sequencing (WES) to evaluate the tumors of patients who achieve clinical benefit, and who have undergone an optional biopsy at the

time of disease progression, in order to determine the acquisition of novel genomic alterations from activation of other signaling pathways and/or from epigenomic changes. We expect to generate at least one *MYBL1*-rearranged PDX model, because about 10% of ACCs harbor *MYBL1* fusions and take rates are about 50-60%. A second PDX model will also be generated from ACC tumors with primary or secondary resistance to tretinoin.

### 9.2.2 Specimen Processing and Analysis

We will first determine the cancer fraction of ACC in circulating tumor (ct) or cell-free (cf)DNA across disease stages. We will isolate cfDNA from the blood of ACC patients treated with tretinoin, before treatment, and at the time specified in the study calendar. The serum from all of these samples will be isolated, sequencing libraries prepared, and next-generation sequencing performed. Data will be segmented, normalized and bias-corrected, using a custom pipeline. The ACC fraction and the total amount of ACC-derived DNA in cfDNA will be determined at the above time points. The ACC-derived cfDNA fraction, and the total circulating ACC DNA concentration, will be correlated with established clinical parameters of ACC disease burden. In selected patients, we will determine ACC DNA fraction and concentration at very early time points to quantify rapid increases of cfDNA as a consequence of the effective killing of ACC cells, as well as later time points. We will establish whether cfDNA can be used as a quantitative tumor marker of treatment response, identify the copy-number variations in cfDNA, and quantify how many subclones have a distinct copy-number profile. The TITAN algorithm [49] or other computational analysis tools will be applied to determine the clonal composition of ACC-derived cfDNA, and the outgrowth over time of drug-resistant subclones will be quantified. These data should reveal the clonal evolution of ACC following tretinoin treatment over time and will define copy-number events that are associated with developing drug resistance.

We will use deep sequencing of cfDNA or CTCs to determine the changes of clonal composition in

ACC during tretinoin treatment. We plan to determine the somatic resistance mutations or other genetic aberrations in cfDNA and CTCs that occur following tretinoin treatment. To this end, we will perform next generation sequencing of DNA or RNA from CTCs or of cfDNA, and also of CD45+ cells from peripheral blood as matched controls. Somatic mutations can be determined using the Mutect algorithm [50], copy-number variations can be determined using Recapseq, and subclonality and cancer cell fraction of all mutations can be evaluated by the Absolute algorithm [51]. The concordance between cfDNA or CTCs and tumor tissue biopsies of ACC will be assessed for the time points detailed in the study calendar. Computational down sampling of these data will define the sequencing depth at which differences can be detected between cfDNA and tissue biopsy of ACC cells.

## 10. STUDY CALENDAR

Baseline evaluations are to be conducted within **28 days** prior to study registration (except for pregnancy test and baseline tumor biopsy, as detailed below). If these screening assessments occur 3 days before start of study treatment, then they may serve as the baseline Cycle 1 Day 1 values. Scans must be done within **28 days** prior to study registration.

As detailed in the *Study Calendar*, a negative pregnancy test in women of child-bearing potential must be documented within 72 hours before the first dose of study medication.

A baseline tumor biopsy, obtained within **28 days** before starting protocol therapy, is also required if tumor tissue is safely accessible. A second, on-treatment tumor biopsy sample will be obtained at the end of Cycle 2, within 14 days of Cycle 3 Day 1. A third (optional) biopsy will be performed if deemed safe or feasible at the time of confirmed disease progression (if that is the reason for coming off treatment).

Baseline laboratory evaluations must be completed **within 14 days** prior to study registration. In the event that the participant's condition is deteriorating, laboratory evaluations should be repeated within 48 hours of treatment initiation of the next cycle of therapy.

Assessments must be performed prior to administration of any study agent. Study assessments and agents should be administered within  $\pm 3$  days of the protocol-specified date, unless otherwise noted.

	Screening A	C1, D1	C2, D1	C2, D16-28	C3 and subsequent cycles	End of protocol Treatment Visit B	Post end of protocol treatment
Tretinoin C		X	X		X		
Informed consent	X						
Demographics	X						
Medical history	X						
Concurrent meds	X	X-----X					
Physical exam	X	X	X		X	X	
Vital signs	X	X	X		X	X	
Height	X						
Weight D	X	X	X		X	X	
Performance status E	X	X	X		X	X	
Hematology labs, coagulation profile F	X	X	X		X	X	
Serum chemistries and lipid panel G	X	X	X		X	X	X
ECG	X						
Tumor biopsy H	X			X H		X H	
Research blood collection I	X		X		X I	X	
Adverse event evaluation J		X-----X					X
Tumor measurements K	X	Tumor measurements are repeated every 8 weeks . Documentation (radiologic) must be provided for participants removed from study treatment for progressive disease.					X K
B-HCG L	X L						

- A. Baseline study evaluations are conducted within 28 days prior to study registration. If screening assessments are 3 days before the start of the start of study treatment, then they may serve as Cycle 1 Day 1 values. Baseline laboratory testing must be completed prior to 14 days of study registration.
- B. The reason for protocol treatment removal and the date the participant was removed from protocol treatment must be documented in the study-specific case report form (CRF). Off protocol treatment visit is to occur within 30 days of final administration of study treatment. End of treatment assessments do not have to be repeated if the same assessments were performed within 7 days prior to the visit.
- C. Tretinoin is dosed at 45 mg/m^2/day divided into two daily doses for days 1 through 14 of a 28-day cycle (tretinoin will be held on days 15 through 28 of every cycle) until disease progression or unacceptable toxicity ensues in **Cohort 1**; tretinoin is dosed at 45 mg/m^2/day divided into two daily doses continuously during a 28-day cycle until disease progression or unacceptable toxicity in **Cohort 2**. Following the first cycle of therapy, tretinoin cycles continue every 28 days or every 4-weeks. The pills should be taken with food (preferably with a fat-containing meal). Patients are required to complete a study drug diary and return the diary at the start of each Cycle (beginning with Cycle 2), and at the end of treatment.
- D. Recorded in kilograms (kg) as the patient's actual (not ideal or adjusted) body weight.
- E. Using ECOG performance status scale of 0-5 (*see Appendix A*).
- F. Hematology laboratory studies should include: CBC with differential and coagulation profile (PT/INR and aPTT).
- G. Serum chemistries should include: a comprehensive metabolic panel with phosphorus and magnesium levels (as appropriate), and a non-fasting lipid panel to include a triglyceride, LDL, HDL, and total cholesterol values.
- H. If tumor is accessible by surgical or percutaneous approach, a tumor biopsy should be performed at the following time points: (1) at baseline, within 28 days of Cycle 1 Day 1 of protocol therapy (ideally as close to administration of Cycle 1 Day 1 therapy as possible) but before the administration of the first dose of study treatment. (2) After cycle 2 (8 weeks on treatment), within 14

days of the start of Cycle 3 Day 1 of protocol therapy – providing the procedure is considered safe, feasible, and accessible at the discretion of the treating investigator. (3) Patients may also be offered an optional end-of-treatment biopsy if the reason for discontinuation was progressive disease – again if safe and feasible.

- I. Research blood sample collections should occur at the following time points: (1) at baseline, within 14 days prior to Cycle 1 Day 1 of protocol therapy (ideally as close to administration of Cycle 1 Day 1 therapy as possible), (2) at the beginning of every new Cycle, following C1 (expected to occur every 28-days) for the first 12 cycles or 1 year on treatment.
- J. Adverse event monitoring should utilize CTCAE version 5.0.
- K. Radiographic evaluations should include contrast-enhanced CT imaging of the chest, abdomen, and pelvis; Contrast-enhanced MR imaging of the abdomen may replace CT abdomen and pelvis if further characterization of liver metastases is preferred (at the discretion of the treating physician). A neck CT with contrast should be obtained if appropriate: such as individuals with a history of ACC that arose in the head and neck, or with residual locoregional disease in the head and neck region. CT head or brain imaging is not required. PET-CT imaging can be considered in lieu of CT imaging at any given radiologic assessment, but both studies are often not required. Assessment will be made at baseline and participants will be followed for best overall response and development and documentation of first disease progression and for survival every 8 weeks throughout the course of the trial for 3 years from the time of study registration. Post end of protocol treatment, if first disease progression has not been documented, tumor assessments are to continue every 8 week until first disease progression. After first disease progression, patients will be followed every 8 weeks for survival (by phone) until death or 3 years from study registration (whichever occurs first).
- L. Female subjects of childbearing potential should have a negative urine or serum pregnancy test within 14 days of study registration. Female subjects of childbearing potential should have a negative urine or serum pregnancy test repeated **within 72 hours** prior to receiving the first dose of study medication. If the urine test is positive or cannot be confirmed as negative, a serum pregnancy test will be required. Women who could potentially become pregnant while undergoing treatment on this protocol must be willing to use 2 methods of contraception.

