  - AST(SGOT)/ALT(SGPT)  $\leq 2.5\text{x}$  institutional ULN or  $\leq 5\text{x}$  ULN for those with liver metastases
  - serum creatinine  $\leq 1.5\text{x}$  ULN

OR

  - creatinine clearance  $\geq 60 \text{ mL/min/1.73 m}^2$  for participants with creatinine levels above  $1.5\text{x}$  ULN
  - coagulation profile INR  $\leq 1.5\text{x}$  ULN unless the participant is receiving an anticoagulant
  - triglyceride level  $< 500 \text{ mg/dL}$  or  $< 5.7 \text{ mmol/L}$
  - cholesterol level  $< 400 \text{ mg/dL}$  or  $< 10.34 \text{ mmol/L}$
9. Baseline tumor measurements must be documented from imaging within 28 days prior to study registration. Other non-laboratory tests must be performed within 28 days prior to study registration.
10. Female subjects of childbearing potential should have a negative urine or serum pregnancy test within 14 days of study registration. Female subjects of childbearing potential should have a negative urine or serum pregnancy test repeated within 72 hours prior to receiving the first dose of study medication. If the urine test is positive or cannot be confirmed as negative, a serum pregnancy test will be required.
11. Female and male subjects of childbearing potential must agree to use an adequate method of contraception (hormonal or barrier method of birth control; abstinence) prior to study entry, for the duration of study participation, and 4 months after completion of tretinoin administration. Contraception is required before starting the first dose of study medication through 120 days after the last dose of study medication. Note: Abstinence is acceptable if this is the usual lifestyle and preferred contraception for the subject. **There is a significant risk of fetal malformation if pregnancy occurs while on tretinoin at any dose level, even if for short exposure periods.**
12. Be willing and able to provide written informed consent for the trial.

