## 5.2 Pre-Treatment Criteria

### 5.2.1 Cycle 1, Day 1

Eligibility and exclusion criteria are provided in *Section 3*. These criteria will be assessed within 28 days of the first day of study treatment to establish eligibility and baseline values.

Informed consent will be obtained after the study has been fully explained to the subject and before the conduct of any screening procedures or assessments. If screening assessments occur within 3 days before start of study treatment, then they may serve as the baseline Cycle 1 Day 1 visit, and Cycle 1 Day 1 labs do not need to be performed.

Demographic information and baseline characteristics will be collected at the Screening Visit. Standard demographic parameters include age, sex, and race/ethnicity (recorded in accordance with prevailing regulations). Baseline characteristics will include ECOG performance status (*Appendix A*), disease status, medical histories, and prior and concomitant medications.

Additional testing required, as per *Section 10*, includes: hematology panel (see **Table 1**), chemistry panel, fasting lipid panel, coagulation panel, urine or serum HCG (in women of childbearing potential; see *Section 3* for when serum HCG testing is required), and an ECG.

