#### 5.2.2 Subsequent Cycles

Reasonable effort should be made to conduct study visits on the day scheduled ( $\pm 3$  days).

Any changes from screening clinical evaluation findings that meet the definition of an adverse event (AE) will be recorded on the AE page of the eCRF.

The participants ECOG performance status, weight (in kilograms), vital signs, interval history since the last visit, and physical examination are performed at each study visit. Concomitant medications should also be reviewed at each study visit. In addition, the adverse event (AE) grid should be completed at each study visit. All laboratory values should be reviewed before proceeding with an additional cycle of treatment. Participants will undergo every-28 day or every 4-week assessments while on study (which coincides with the start of each cycle of therapy). The drug diary for the prior cycle should be reviewed at each study visit by the clinical staff.

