7.3.3 Serious Adverse Events

7.3.3.1 Definition

A **Serious Adverse Event (SAE)** is any untoward medical occurrence that at any dose:

- Results in death
- Is life-threatening (defined as an event in which the participant was at risk of death at the time of the event; it does not refer to an event which hypothetically might have caused death if it were more severe)
- Requires inpatient hospitalization or causes prolongation of existing hospitalization (see **NOTE** below)
- Results in persistent or significant disability/incapacity
- Is a congenital anomaly/birth defect
- Is an important medical event (defined as a medical event(s) that may not be immediately life-threatening or result in death or hospitalization but, based upon appropriate medical and scientific judgment, may jeopardize the subject or may require intervention [eg, medical, surgical] to prevent one of the other serious outcomes listed in the definition above.) Examples of such events include, but are not limited to, intensive treatment in an emergency room or at

home for allergic bronchospasm; blood dyscrasias or convulsions that do not result in hospitalization.)

- Suspected transmission of an infectious agent (eg, pathogenic or nonpathogenic) via the study drug is an SAE.

Although pregnancy, overdose, potential drug-induced liver injury (DILI), and cancer are not always serious by regulatory definition, these events must be handled as SAEs.

Any component of a study endpoint that is considered related to study therapy should be reported as an SAE (eg, death is an endpoint, if death occurred due to anaphylaxis, anaphylaxis must be reported).

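### Pregnancy testing stops at the first tretinoin dose: two tests are scheduled before it and none in up to 24 months of treatment with a known teratogen

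*Protocol*

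**What the plan says.** Section 3.1 item 10 asks women of childbearing potential for a negative test within 14 days of registration and a second, "negative urine or serum pregnancy test repeated within 72 hours prior to receiving the first dose of study medication". Footnote L of the Section 10 calendar says the same, and the text above the grid says "a negative pregnancy test in women of child-bearing potential must be documented within 72 hours before the first dose of study medication". In the grid, the B-HCG row carries one mark, under Screening. Section 5.2.1 lists HCG among the tests before Cycle 1 Day 1 and refers back to Section 3.

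For later cycles, Section 5.2.2 says "All laboratory values should be reviewed before proceeding with an additional cycle of treatment" and that "interval history since the last visit, and physical examination are performed at each study visit". Neither it nor Sections 5.2.3 and 5.2.4 (additional on-treatment assessments and end of treatment) names a pregnancy test.

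On the hazard, Section 3.1 item 11 states: "There is a significant risk of fetal malformation if pregnancy occurs while on tretinoin at any dose level, even if for short exposure periods". On prevention, the same item requires contraception until 120 days after the last dose, and footnote L adds: "Women who could potentially become pregnant while undergoing treatment on this protocol must be willing to use 2 methods of contraception". Pregnancy is a reason to stop therapy in Section 5.5, and Section 7.3.3.1 says "pregnancy, overdose, potential drug-induced liver injury (DILI), and cancer are not always serious by regulatory definition, these events must be handled as SAEs". Section 5.1 plans treatment for 24 months.

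**The concern.** The protocol describes a serious fetal hazard that does not depend on dose or on long exposure, and it has rules for what happens once a pregnancy is known. It schedules nothing after the first dose that would make one known. The stopping rule in Section 5.5 and the SAE rule in Section 7.3.3.1 therefore depend on a patient's own report or on a chance clinical finding.

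Section 5.2.2 makes laboratory review a condition for starting each new cycle, but no pregnancy result is among the required laboratory values. The history and examination at each visit may miss an early pregnancy. Malaise and fatigue are common tretinoin effects according to Section 2.2.1.3, so early symptoms could be put down to the drug; that last step is an inference, not a statement in the protocol.

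What is at stake is avoidable continued fetal exposure. The primary endpoint, the two-stage rule and the Cohort 2 confidence limits are untouched.

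**Working it through.** There is no plan figure to reproduce. The check is a reading of every place where testing is scheduled, followed by a count.

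**Where a test is scheduled**

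| Place in the protocol | Pregnancy test |
|---|---|
| 3.1 item 10; footnote L | Two, both before the first dose |
| 5.2.1, Cycle 1 Day 1 | HCG, referring back to Section 3 |
| 10, B-HCG row | One mark, Screening, carrying footnote L |
| 5.2.2, later cycles | None |
| 5.2.3, on-treatment assessments | None |
| 5.2.4, end of treatment | None |

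A damaged table does not explain the single mark. Footnote L and Sections 5.2.2 to 5.2.4 are running text and agree with it. The count is two tests before the first dose and none after it.

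**How many cycle starts have no test**

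- Inputs: 24 months of treatment and 28-day cycles (Section 5.1).
- 24 months = 2 × 365 = 730 days; 730 / 28 = 26.07, so about 26 cycles.
- Starts after the first: Cycle 2 to Cycle 26 = 25.

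**What testing on each later Day 1 and at end of treatment would add, per woman of childbearing potential**

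- Full 24 months: 25 + 1 = 26 tests.
- Stopping in Cycle 1: no Cycle 2 Day 1, so 1 test, if the end-of-treatment visit takes place.

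**Cohort 2 (n = 6), assuming 0 to 6 such women, since the documents give no number**

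- All stop in Cycle 1: 0 to 6 × 1 = 0 to 6 tests.
- All complete 24 months: 0 to 6 × 26 = 0 to 156 tests.
- Cohort 1 would add only patients still on drug, a number the documents do not give.

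**Spacing of tests under the fix**

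- No hold: 28 days. With the ±3-day window at both visits, 28 − 6 = 22 to 28 + 6 = 34 days.
- Section 6 allows a toxicity hold of up to 28 days. If a hold moves Day 1, which the protocol does not say, the gap is 28 + 28 = 56 days, or 56 + 6 = 62 with the windows.

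**A lighter schedule for comparison**

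- Every second cycle, with the 8-week scans: Cycles 3, 5, …, 25 = 12 tests, plus end of treatment = 13. Every other cycle start would still have no test.

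**The case against.** The strongest reply is that the protocol manages this hazard by preventing conception, and that the warning in item 11 belongs to the contraception criterion. Two methods are required, cover runs to 120 days after the last dose, pregnant women are excluded, and a known pregnancy stops treatment. A Day 1 test finds a pregnancy only after exposure has begun, and at the spacing above it cannot prevent the short exposure the warning describes. In Cohort 2, dosing is continuous, so Day 1 is not a true restart after a break as it is in Cohort 1.

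All of that is correct, and it limits what testing can achieve: it shortens exposure rather than preventing it. It does not remove the reason to test. The contraception wording is also uneven. Item 11 appears satisfied by a hormonal or barrier method, while exclusion 7 and footnote L ask for two methods, and Appendix B lists some oral contraceptives among drugs that may interact with tretinoin, without saying in which direction.

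Second, Section 7.1 refers to a package insert attached to the protocol. Neither that insert nor the consent pages were available, and they may contain testing instructions. This stands as a limit: the finding covers the calendar, its footnotes and Section 5.2 only.

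Third, the high counts need 24 months on drug, and 156 also needs all six Cohort 2 patients to be women of childbearing potential. Section 13 reports low efficacy in Cohort 1, so long treatment may be uncommon. The counts are ceilings and should be read as such.

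Finally, Table 1 and footnotes F and G omit HCG even at baseline, so their silence about later cycles proves nothing. The finding does not need them.

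**Conclusion.** The concern holds and should be fixed. Within the calendar, its footnotes and Section 5.2, no pregnancy test is scheduled after the first dose, leaving up to about 25 cycle starts untested over the planned 24 months. The gap in the schedule is the same for both cohorts, although the exposure pattern differs.

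The practical size is uncertain. It depends on how many women of childbearing potential are treated, which may be none, and on how long they stay on drug. Sites may test on their own initiative, but the sections examined do not require it. This is a point about participant safety, with no effect on efficacy analysis or decisions.

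**What to change.** In the Section 10 calendar, for women of childbearing potential only, mark B-HCG at Cycle 2 Day 1, at Day 1 of Cycle 3 and every later cycle, and at the end-of-treatment visit. Use urine, or an add-on to serum already drawn, and review the result before that cycle's first dose. If a hold moves Day 1, the test moves with it and still precedes redosing. If urine is positive or inconclusive, do a serum test, as item 10 already provides, and hold tretinoin until the result is known. Bring footnote L and Sections 5.2.2 and 5.2.4 into line. Sections 5.5 and 7.3.3.1 need no change.

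The documents examined set no testing frequency. Day 1 is proposed because treatment is reviewed then and Section 5.1 already requires a lipid panel. Testing every second cycle is possible but halves the coverage.

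The cost is a calendar and footnote amendment, an inexpensive test at visits that already take blood, and an occasional short delay from a false positive. No visit, staff or invasive procedure is added.
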